17. QUALITY OF LIFE ANALYSIS

Not Applicable.

18. SAFETY OUTCOMES

All outputs for safety outcomes will be based on the SAF population.

There will be no statistical comparisons between the treatment groups for safety data, unless otherwise specified with the relevant section.

Document: \\needc-vnasc01\Biosdata\Menarini\NebAm\ZZA67778\Biostatistics\Documentation\SAP\SAP_Menarini_MEIN21AmNe-Hyp001_Final_V1.0

Author: [name]

Version Number:

Final V1.0

Version Date:

11Nov2022

Template No.: CS_TP_BS016 Revision 7

Reference: CS_WI_BS005

Effective Date: 01Nov2021

18.1. Adverse Events

Adverse Events (AEs) will be coded using Medical Dictionary for Regulatory Activities (MedDRA) central coding dictionary, Version 25.0 or latest.

Treatment emergent adverse events (TEAEs) are defined as new AEs that occur on or after the date/time of the first administration of study medication (i.e., monotherapy and/or combination therapy) or worsen if an AE started prior to the start of first administration of study medication.

TEAEs that occurred or worsened on or after the date/time of the first administration of Monotherapy but before the date/time of the first administration of Combination Therapy will be summarized under “Monotherapy”.

TEAEs that occurred or worsened on or after the date/time of the first administration of Combination Therapy will be summarized under “Combination Therapy”.

See Appendix 2 for handling of partial dates for AEs. In the case where it is not possible to define an AE as treatment emergent or not, the AE will be classified by the worst case, i.e., treatment emergent.

An overall summary of number of subjects within each of the categories described in the subsection below, will be provided as specified in the templates.

Listings will include TEAEs and Non-TEAEs.

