
 
weeks.
 
To assess the antihypertensive efficacy of the extemporaneous combination of NEB 5 mg with AML 5 mg or AML 10 mg by evaluating the patients who achieve BP goal (sitting BP <130/80 mmHg) at Visit 2 (Week 0), at Visit 3 (Week 4), and at Visit 4 (Week 8).
 
	
 
Number and proportion of patients achieving the BP goal (sitting SBP/DBP <130/80 mmHg) at Visit 2 (Week 0), Visit 3 (Week 4) and Visit 4 (Week 8).
 
	The proportion of patients at target is a very important clinical indicator of therapeutic success.
• To assess the compliance to the treatment (percentage of actual doses taken versus doses to be taken) at Visit 2 (Week 0), at Visit 3 (Week 4), and at Visit 4 (Week 8).	doses taken/doses to be taken) at Visit 2 (Week 0), Visit 3 (Week	Monitoring compliance is extremely important to better evaluate the efficacy and tolerability of the extemporaneous combination.
• To evaluate the safety and tolerability of the monotherapies (NEB 5 mg and AML 5 mg) and of the extemporaneous combinations (NEB 5 mg and AML 5mg or AML 10 mg) after 8 weeks of treatment.	
 
Safety and tolerability of the monotherapies (NEB 5 mg and AML 5 mg) and of the extemporaneous combinations (NEB 5 mg and AML 5mg or AML 10 mg) will be measured by incidence, intensity (severity), seriousness of Adverse Events (AEs) during the study period, (screening, run-in period and assessment period), relationship to the study treatments, Adverse events of special interest, clinically significant abnormal change in vital signs, electrocardiogram (ECG) (only at Visit 1 and Visit 4), laboratory parameters (if applicable) at Visit
 
	Incidence of adverse drug reactions (ADRs), AEs, serious adverse events (SAEs), vital signs, physical examination, ECG needs to be studied to address safety and tolerability of the extemporaneous combination.

MENARINI	Corporate Medical Department		ent
	Protocol Template		
Identification Number	Version Number	State	Effective date
FORM-000050125	2.0, CURRENT	Effective	08 Jan, 2021

OBJECTIVES	ENDPOINTS	JUSTIFICATION FOR ENDPOINTS
	2 (Week 0), Visit 3 (Week 4), and Visit 4 (Week 8).	
Exploratory		

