### 5 STUDY DESIGN

This is a Phase IV, interventional, open-label, multicenter, multinational study with 2 study periods (a run-in period of 4 weeks and an assessment period of 8 weeks) to assess efficacy and safety of the extemporaneous combination of Nebivolol and Amlodipine in Grade 1 - 2 hypertension patients versus each monotherapy.

The study will be conducted in approximately 25 investigational clinical sites in Bulgaria, Poland, and Ukraine. The total study duration is 12 weeks including a run-in period of 4 weeks and an assessment period of 8 weeks.

Screening Visit 1 (Week -4): At Visit 1, after providing the informed consent, patients with Grade 1 - 2 hypertension (SBP ranging from  $\geq$ 140 to  $\leq$ 179 mmHg and DBP ranging from  $\geq$ 90 to  $\leq$ 109 mmHg) who were on treatment with any BBs or CCBsc including NEB 5 mg or AML 5 mg for at least one month prior to Visit 1 will be screened for eligibility. The eligibility for Grade 1 - 2 hypertension will be based on the 2018 ESC/ESH guidelines, and the BP criteria is defined as mean sitting SBP  $\geq$ 140 mmHg and  $\leq$ 179 mmHg and/or mean sitting DBP  $\geq$ 90 mmHg and  $\leq$ 109 mmHg.

Run-in period from Visit 1 (Week -4) to Visit 2 (Week 0): On the same day of the Screening visit, the eligible patients will enter into a run-in period of 4 weeks after screening, during which:

- Patients receiving NEB 5 mg or AML 5 mg will continue the same therapy for 4 weeks.
- Patients on any other BBs or CCBsc will be switched to NEB 5 mg or AML 5 mg.

Patients entering this phase in therapy with NEB 5 mg or AML 5 mg should be in a 1:1 ratio.

Assessment period from Visit 2 (Week 0) to Visit 4 (Week 8): After 4 weeks ( $\pm$ 2 days) of run-in period of monotherapy, the BP will be further assessed (Visit 2). Patients with uncontrolled BP levels (sitting SBP/DBP  $\geq$ 130/80 mmHg) at Visit 2, with the treatment adherence (ranging between 80% to 120%) and who did tolerate the treatment will enter into the assessment period and will be assigned to the extemporaneous combination of NEB 5 mg

MENARINI	Corporate Medical Department		
	Protocol Template		
Identification Number	Version Number	State	Effective date
FORM-000050125	2.0, CURRENT	Effective	08 Jan, 2021

*Study Code:* MEIN/21/AmNe-Hyp/001

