and AML 5 mg. Patients with controlled BP levels (sitting SBP/DBP <130/80 mmHg) and/or who do not tolerate the treatment or have an adherence range below 80% or above 120%, will be withdrawn from the study.

After 4 weeks  $\pm 2$  days in the assessment period, patients BP will be further evaluated at Visit 3: patients with controlled BP levels (sitting SBP/DBP <130/80 mmHg) will continue the same extemporaneous combination, while patients with uncontrolled BP levels will be uptitrated from extemporaneous combination NEB/AML 5/5 mg to extemporaneous combination of NEB/AML 5/10 mg for further 4 weeks.

At the end of the assessment period (8 weeks  $\pm 4$  days), the patients will attend an End of Treatment Visit 4. To correctly evaluate the additional effect of the combination therapy, the number of patients with uncontrolled BP on NEB or AML monotherapy needs to be balanced at Visit 2. In order to maintain a 1:1 ratio during the assessment period, a cap of 110 patients for each treatment arm (ie. NEB and AML) will be included at Visit 2 in order to maintain a balanced number of uncontrolled patients entering the assessment period for each drug. The evaluation will be done every 50 patients. If the rate of entrance in the assessment period for one of the 2 tested drugs will deviate more than 5%, a corrective measure will be initiated: according to the enrolment site statistics, one or more sites will be informed to enroll a greater number of patients being treated with the least represented drug in the assessment period.

A total number of 290 patients will be screened considering 25% of drop-out rate, to obtain approximately 216 completed patients at the end of the study (Visit 4).

Sitting BP will be measured at all visits before blood sampling. BP will be measured in both arms at the Screening visit (Visit 1) in order to detect possible between-arm differences. The arm with the higher mean DBP will be used in all subsequent visits for BP assessment. Blood pressure measurements should be performed as nearly as possible within the same time frame of the day (7:00 to 12:00 a.m.), on the same arm, possibly by the same member of the site staff/personnel, and using the same calibrated equipment at each visit.

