2.2. Secondary Objectives

The secondary objectives are

- To assess the antihypertensive efficacy of the extemporaneous combination of NEB 5 mg with AML 5 mg or AML 10 mg in lowering sitting SBP between Visit 2 (Week 0) and Visit 4 (Week 8) in patients with uncontrolled BP previously treated with NEB 5 mg or AML 5 mg monotherapies for at least 4 weeks.
- To assess the antihypertensive efficacy of the extemporaneous combination of NEB/AML 5/10 mg versus extemporaneous combination NEB/AML 5/5 mg, in lowering sitting DBP and SBP between Visit 3 (Week 4) and Visit 4 (Week 8) in patients with uncontrolled BP previously treated with NEB 5 mg or AML 5 mg monotherapies for at least 4 weeks.
- To assess the antihypertensive efficacy of the extemporaneous combination of NEB 5 mg with AML 5 mg or AML 10 mg by evaluating the patients who achieve BP goal (sitting BP < 130/80 mmHg) at Visit 2 (Week 0), at Visit 3 (Week 4), and at Visit 4 (Week 8).
- To assess the compliance to the treatment (percentage of actual doses taken versus doses to be

Document: \\weedc-vnasc01\Biosdata\Menarini\NebAml\ZZA67778\Biostatistics\Documentation\SAP\SAP_Menarini_MEIN21AmNe-Hyp001_Final_V1.0

Author: [name]

Version Number:

Final V1.0

Version Date:

11Nov2022

Template No.: CS_TP_BS016 Revision 7

Reference: CS_WI_BS005

Effective Date: 01Nov2021

taken) at Visit 2 (Week 0), at Visit 3 (Week 4), and at Visit 4 (Week 8).

- To evaluate the safety and tolerability of the monotherapies (NEB 5 mg and AML 5 mg) and of the extemporaneous combinations (NEB 5 mg and AML 5mg or AML 10 mg) after 8 weeks of treatment.

2.3.Exploratory Objectives

The exploratory objectives are

- To assess change in mean sitting DBP and SBP between Visit 1 (Week -4) and Visit 2 (Week 0), Visit 3 (Week 4) and Visit 4 (Week 8):
 1. In the group of patients who were on NEB 5 mg and AML 5 mg at Visit 1 and continued to be on the same therapies.
 2. In the group of patients who switched to NEB 5 mg or AML 5 mg from any other BBs or CCBs at Visit 1.
- To assess the change in mean sitting DBP and SBP between Visit 2 (Week 0) and Visit 3 (Week 4) for uncontrolled patients at Visit 3 (Week 4).
- To assess the antihypertensive efficacy of the extemporaneous combination of NEB 5 mg with AML 5 mg or AML 10 mg by evaluating the number of patients achieving the BP goal (sitting BP <130/80 mmHg) at Visit 2 (Week 0), Visit 3 (Week 4) and Visit 4 (Week 8):

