3. STUDY DESIGN

3.1. General Description

This is a Phase IV, interventional, open-label, multicenter, multinational study with 2 study periods (a run-in period of 4 weeks and an assessment period of 8 weeks). Patients with hypertension with systolic blood pressure (SBP) ranging from ≥ 140 to ≤ 179 mmHg and diastolic blood pressure (DBP) ranging from ≥ 90 to ≤ 109 mmHg on treatment with any beta-blockers (BBs) or calcium channel blockers (CCBs) including NEB 5 mg or AML 5 mg for at least one month prior to Visit 1 will be screened for eligibility. On the same day of the Screening visit, eligible patients will enter into a run-in period after screening, during which:

- Patients receiving NEB 5 mg or AML 5 mg will continue the same therapy for 4 weeks.
- Patients on any other BBs or CCBs will be switched to NEB 5 mg or AML 5 mg.

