18.1.2. TEAEs Leading to Discontinuation of Study Medication

TEAEs leading to permanent discontinuation of study medication (i.e., monotherapy and/or combination therapy) are those events for which “Action Taken with Study Treatment” is recorded as “Drug withdrawal” on the Adverse Event page of the eCRF.

For TEAEs leading to discontinuation of study medication, summaries of incidence rates (frequencies and percentages) by SOC and PT will be prepared.

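### Crude adverse-event percentages for about 4 weeks of monotherapy and up to 8 weeks of combination, the latter in patients selected at Visit 2, cannot be read side by side without time-adjusted rates

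*SAP*

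**What the plan says.** Protocol section 5 gives the purpose as "to assess efficacy and safety of the extemporaneous combination of Nebivolol and Amlodipine in Grade 1 - 2 hypertension patients versus each monotherapy", and the durations as follows: "The total study duration is 12 weeks including a run-in period of 4 weeks and an assessment period of 8 weeks". The safety objective covers the two monotherapies together with "the extemporaneous combinations (NEB 5 mg and AML 5mg or AML 10 mg) after 8 weeks of treatment" (SAP 2.2; the same objective stands in Protocol section 4).

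Inclusion criterion 1 requires at least 4 weeks on beta-blocker or calcium-channel-blocker monotherapy before screening. At Visit 2, patients with controlled blood pressure leave, as do those "who do not tolerate the treatment or have an adherence range below 80% or above 120%, will be withdrawn from the study". At Visit 3, uncontrolled patients move to 5/10 mg for the last 4 weeks.

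SAP 18.1 assigns events to Monotherapy up to the first combination dose, and after that point "TEAEs that occurred or worsened on or after the date/time of the first administration of Combination Therapy will be summarized under" Combination Therapy. SAP 18.1.1 presents incidence by system organ class and preferred term. SAP 18.1.2 shows what the SAP means by a rate: "summaries of incidence rates (frequencies and percentages) by SOC and PT will be prepared". Under SAP 7, percentages are based on numbers of patients. SAP 14 summarises days of exposure for each therapy, but no adverse-event output uses them. SAP 18 plans no statistical comparison of safety data unless a section says otherwise.

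**The concern.** The two periods differ in length and in who is observed. A window twice as long gives each patient more time to have an event, which raises the combination percentage. The Visit 2 rule removes patients who did badly on monotherapy, which lowers it. A reader who sets the columns side by side, as the purpose against each monotherapy invites, cannot tell whether a difference reflects adding the second drug, the longer window or the selection.

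The objective's duration adds to this. No patient has 8 study weeks on a monotherapy or on 5/10 mg. Only patients controlled at Visit 3 are planned to spend all 8 weeks on 5/5 mg.

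**Working it through.** **1. Durations.** Run-in 4 weeks plus assessment 8 weeks = 12 weeks, which reproduces the protocol's total. Nominal ratio of observation per patient: 8/4 = 2. With the visit windows (28 ± 2 days and 56 ± 4 days) it ranges from 52/30 = 1.7 to 60/26 = 2.3.

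**2. Effect of window length alone.** The documents give no adverse-event rates, so the 4-week risks p below are assumptions. At the same constant hazard, the 8-week risk is 1 − (1 − p)².

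| Assumed 4-week risk | 8-week risk | Ratio |
|---|---|---|
| 2% | 1 − 0.98² = 3.96% | 1.98 |
| 5% | 1 − 0.95² = 9.75% | 1.95 |
| 10% | 1 − 0.90² = 19.0% | 1.90 |
| 20% | 1 − 0.80² = 36.0% | 1.80 |

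At 10%, the visit windows move the second figure between 1 − 0.9^(52/30) = 16.7% and 1 − 0.9^(60/26) = 21.6%.

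**3. Effect of selection.** As an illustration, suppose a fraction f of patients is susceptible with a 4-week risk of 60%, the rest have 8%, susceptible patients with a run-in event leave at Visit 2, and no patient's hazard changes. All of these values are assumptions. Monotherapy risk = 0.60f + 0.08(1 − f). The susceptible share entering the combination period is 0.4f / (0.4f + 1 − f). The 8-week risks are 1 − 0.4² = 84% and 1 − 0.92² = 15.36%. Rates are first events per 100 patient-weeks at risk.

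| f | Monotherapy % | Combination % | Monotherapy rate | Combination rate |
|---|---|---|---|---|
| 5% | 10.6 | 16.8 | 2.81 | 2.30 |
| 10% | 13.2 | 18.3 | 3.55 | 2.54 |
| 20% | 18.4 | 21.6 | 5.12 | 3.07 |

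The percentages rise and the rates fall, although no hazard changed. Not all of the fall is selection, because susceptible patients are also used up within the longer window. At f = 20% with nobody leaving, the 8-week risk is 0.2 × 84% + 0.8 × 15.36% = 29.1%. Weekly hazards are −ln(0.4)/4 = 0.2291 and −ln(0.92)/4 = 0.02085, so mean time at risk is 0.2 × 0.84/0.2291 + 0.8 × 0.1536/0.02085 = 6.63 weeks. That gives 4.39 per 100 patient-weeks, against 5.12 over 4 weeks.

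**4. Which denominator equalises the periods.** Under constant hazard, dividing patients with events by full exposure does not: at 10%, 10/4 = 2.50 against 19/8 = 2.375 per 100 patient-weeks; at 20%, 20/4 = 5.0 against 36/8 = 4.5. Stopping each patient's time at the first event does: at 10%, −ln(0.9)/4 = 2.63 per 100 patient-weeks in both periods.

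**The case against.** The strongest reply is that this is descriptive reporting. The secondary objective asks for an evaluation of the monotherapies and of the combinations and states no contrast between them. SAP 18 plans no safety test, and SAP 14 shows the exposure days. This stands in part. A reader might infer that the plan contains an invalid safety comparison, and the documents do not support that. But the overall purpose names each monotherapy as the reference, and a separate exposure summary does not let anyone rebuild time-at-risk rates by preferred term.

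Four further limits stand:

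- The monotherapy column might be taken for unselected patients. It is not: they had already had at least 4 weeks on a drug from one of the two classes, some on the same drug and dose.
- The factor of 1.8 to 1.95 might be taken as the expected error. It applies only to a pooled combination column under assumed risks. SAP Appendix 1 lists four treatment groups for outputs, and the table templates are not in the text reviewed. A separate 5/10 mg column would cover only about 4 weeks at that dose.
- A same-patient table of run-in weeks against the first four combination weeks might be taken as a fair contrast. It keeps only patients who tolerated monotherapy, so it removes intolerance from the monotherapy side alone and tilts against the combination.
- In the objective, the 8 weeks can be read as qualifying only the combinations, and the endpoint in the same protocol row names the actual study periods. That part is a matter of wording.

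**Conclusion.** The concern holds as a risk of misleading description. Observation per patient is nominally twice as long on the combination (1.7 to 2.3 times within the visit windows), the combination set is selected at Visit 2 on tolerance, adherence and blood pressure, and the SAP text plans only patient percentages. Window length alone would give a ratio of 1.8 to 1.95 in a pooled column at assumed 4-week risks of 5-20% and constant hazard. Selection acts in the opposite direction by an amount that the documents cannot settle, so the net bias has neither a known size nor a known sign. It would be wrong to conclude that the combination will necessarily look worse. With a fixed treatment order and no randomisation, no table can isolate the effect of adding the second drug. The achievable gain is to remove the avoidable duration artefact and make the selection visible.

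**What to change.** In SAP 18.1, keep the existing Safety-population percentages and make these changes:

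1. Add for each period the number of patients with a first treatment-emergent event per 100 patient-weeks at risk, with time censored at the first event or the end of the period. Do not use full SAP 14 exposure as the denominator. Define the end of the monotherapy period for patients who never start the combination.
2. Footnote the adverse-event tables with the period length, the period-specific denominator and the Visit 2 selection rule.
3. Optionally, add a supportive table of the run-in weeks against Visit 2 to Visit 3 in patients who entered the assessment period. Footnote it as conditioned on having tolerated monotherapy and therefore tilted against the combination.
4. Reconcile "after 8 weeks of treatment" in the safety objective with the design's durations: 4 weeks on each study monotherapy, about 4 weeks on 5/10 mg and up to 8 weeks on 5/5 mg.

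The cost is modest programming for an added rate per period, footnotes and possibly one table. Event and dosing dates are already needed for SAP 14 and 18.1, and the primary analysis is untouched. If the database is already locked, Protocol 12.7 allows these outputs as additional analyses. The rates address duration only, and exactly so only if the hazard is constant. They do not correct for selection or for the fixed treatment order.

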18.1.1. All TEAEs

Incidence of TEAEs will be presented by System Organ Class (SOC) and Preferred Term (PT) and broken down further by maximum severity and relationship to study medication (i.e., monotherapy and/or combination therapy).

18.1.1.1. Severity

Severity is classed as mild/ moderate/ severe (increasing severity). TEAEs starting after the first dose of study medication (i.e., monotherapy and/or combination therapy) with a missing severity will be classified as severe. If a subject reports a TEAE more than once within that SOC/ PT, the AE with the worst-case severity will be used in the corresponding severity summaries.

Document: \\ieedc-vnasc01\Biosdata\Menarini\NebAml\ZZA67778\Biostatistics\Documentation\SAP\SAP_Menarini_MEIN21AmNe-Hyp001_Final_V1.0

Author: [name]

Version Number:

Final V1.0

Version Date:

11Nov2022

Template No.: CS_TP_BS016 Revision 7

Reference: CS_WI_BS005

Effective Date: 01Nov2021

18.1.1.2. Relationship to Study Medication

Relationship, as indicated by the Investigator, is classed as “Not Related”, “Related” (increasing severity of relationship). A “related” TEAE is defined as a TEAE with a relationship to study medication (i.e., monotherapy and/or combination therapy) as “Certain Related”, “Probable Related”, “Possible Related” or “Unassessable” to study medication. TEAEs with a missing relationship to study medication will be regarded as “Probable Related” to study medication. If a patient reports the same AE more than once within that SOC/ PT, the AE with the worst-case relationship to study medication will be used in the corresponding relationship summaries.

18.1.2. TEAEs Leading to Discontinuation of Study Medication

TEAEs leading to permanent discontinuation of study medication (i.e., monotherapy and/or combination therapy) are those events for which “Action Taken with Study Treatment” is recorded as “Drug withdrawal” on the Adverse Event page of the eCRF.

For TEAEs leading to discontinuation of study medication, summaries of incidence rates (frequencies and percentages) by SOC and PT will be prepared.

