	
 
Safety and tolerability of the monotherapies (NEB 5 mg and AML 5 mg) and of the extemporaneous combinations (NEB 5 mg and AML 5 mg or AML 10 mg) will be measured by incidence, intensity (severity), seriousness of Adverse Events during the study period, (screening, run-in period and assessment period), relationship to the study treatments, Adverse events of special interest, clinically significant abnormal change in vital signs, electrocardiogram (only at Visit 1 and Visit 4), laboratory parameters (if applicable) at Visit 2 (Week 0), Visit 3 (Week 4), and Visit 4 (Week 8).
 
	
	Exploratory Endpoints:	
	• Change in mean sitting DBP and SBP between Visit (Week -4) and Visit 2 (Week 0), Visit 3 (Week 4) an Visit 4 (Week 8):	
	• In the group of patients who were on NEB 5 mg and	

MENARINI	Corporate Medical Department				
	Protocol Template				
Identification Number	Version Number	State	Effective date		
FORM-000050125	2.0, CURRENT	Effective	08 Jan, 2021		

	AML 5 mg at Visit 1 and continued to be on the
	
 
same therapies.
 
In the group of patients who switched to NEB 5 mg or AML 5 mg from any other BBs or CCBs at Visit 1.
 

	
 
Change in mean sitting DBP and SBP for uncontrolled patients at Visit 3 (Week 4), between Visit 2 (Week 0) and Visit 3 (Week 4).
 
Number and proportion of patients achieving the BP goal (sitting SBP/DBP <130/80 mmHg) at Visit 2 (Week 0), Visit 3 (Week 4), and Visit 4 (Week 8): 
 
In the group of patients who were on NEB 5 mg and AML 5 mg at Visit 1 (Week -4) and continued to be on the same therapies.
 
 
 

	
 
In the group of patients who switched to NEB 5 mg or AML 5 mg from any other BBs or CCBs at Visit 1 (Week- 4).
 

	• Number and proportion of patients divided into subgroups according to the hypertension grade, the presence of diabetes and/or of hypercholesterolemia achieving the BP goal (sitting SBP/DBP <130/80 mmHg) at Visit 2 (Week 0), Visit 3 (Week 4), and Visit 4 (Week 8):
	
 
In the group of patients who were on NEB 5 mg and AML 5 mg at Visit 1 (Week -4) and continued to be on the same therapies.
 

	
 
In the group of patients, who switched to NEB 5 mg or AML 5 mg from any other BBs or CCBs at Visit 1 (Week -4).
 

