	to the hypertension grade, the presence of diabetes and/or of hypercholesterolemia achieving the BP goal (sitting SBP/DBP <130/80 mmHg) at Visit 2 (Week 0), Visit 3 (Week 4) and Visit 4 (Week 8):	
	
 
in the group of patients who were on NEB 5 mg and AML
 
5 mg at Visit 1 (Week -4) and continued on the same therapies.
 
	
	
 
in the group of patients, who switched to NEB 5 mg or AML
 
5 mg from any other BBs or CCBs at Visit 1 (Week -4).
 
	
Safety	Incidence, intensity (severity), seriousness of AEs during the study period, (screening, run-in period and assessment period), relationship to the study treatments, AEOSIs, abnormal/unexpected change in vital signs, ECG (only at Visit 1 and Visit 4), Laboratory parameters (if applicable), and use of concomitant medications at Visit 2 (Week 0), Visit 3 (Week 4) and Visit 4 (Week 8).	Safety population
pressure; CO	AE = adverse event; AEOSI = adverse event of special interest; AML = Amlodipine; BB $CB =$ calcium channel blocker; DBP = diastolic blood pressure; ECG = electrocardiogram at; NEB = nebivolol; PP = per-protocol; and SBP = systolic blood pressure.	-

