### 12.5.6 Safety analysis

Safety analysis will be based on the safety population.

Adverse events recorded during the study will be mapped to a system organ class and preferred term using the current Medical Dictionary for Regulatory Activities. Treatmentemergent adverse events are defined as new AEs that occur on or after the date/time of the first administration of study medication or worsen if an AE started prior to the start of first administration of study medication.

Summaries will be provided for treatment-emergent adverse event related AEs, SAEs, AEs based on their severity, deaths, and AEs leading to discontinuation from study.

Laboratory, ECG, Physical examination, and Vital signs data will be summarized by each visit for absolute values as well as change from baseline. The number of normal, abnormal not clinically significant and abnormal clinically significant values on each parameter will be summarized for ECG and Physical examination using shift tables.

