18.7. Other Safety Assessments

No other safety assessment will be collected for this study.

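### SAP 18.1.2 tabulates events leading to drug withdrawal where protocol 12.5.6 plans events leading to study discontinuation, and SAP 18 has no summary of events of special interest; SAP 3.3 declares neither change

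*SAP*

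**What the plan says.** **Discontinuation.** The safety summaries listed in protocol 12.5.6 end with "deaths, and AEs leading to discontinuation from study". SAP 18.1.2 defines its set by stopping the drug: "TEAEs leading to permanent discontinuation of study medication (i.e., monotherapy and/or combination therapy) are those events for which" the action taken with treatment is entered as drug withdrawal on the adverse event page of the eCRF. Its output is then stated: "For TEAEs leading to discontinuation of study medication, summaries of incidence rates (frequencies and percentages) by SOC and PT will be prepared".

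**Leaving at Visit 2.** Under protocol section 5, patients with controlled blood pressure and those "who do not tolerate the treatment or have an adherence range below 80% or above 120%, will be withdrawn from the study". This decision falls at the end of the 4-week monotherapy run-in.

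**Special-interest events.** The secondary safety endpoint in the protocol synopsis includes "relationship to the study treatments, Adverse events of special interest, clinically significant abnormal change in vital signs". The safety row of protocol 12.4 repeats the component as an analysis variable for the Safety population: "relationship to the study treatments, AEOSIs, abnormal/unexpected change in vital signs". Protocol sections 4 and 8.2 also name it. SAP 18.1 has subsections for all treatment-emergent events (with severity and relationship), discontinuation of medication, serious events and fatal events. It has none for special-interest events. SAP 18.7 closes the safety section with "No other safety assessment will be collected for this study".

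**Declared changes.** SAP 3.3 lists five departures from the protocol: the McNemar test, the Per-Protocol definition, the Enrolled definition, the populations for compliance, and the populations for the exploratory analyses. Neither point above is among them.

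**The concern.** Tolerability of the two monotherapies is a stated secondary objective, and for the run-in it is largely expressed by who had to leave because of an event. The protocol's summary is keyed to leaving the study; the SAP's is keyed to a drug-action field on the event record. The two sets can differ exactly where the design removes intolerant patients, because at Visit 2 the run-in course is ending anyway and investigators may not see the drug as withdrawn. A discontinuation table that omits some of these patients would make monotherapy look better tolerated than it was.

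For special-interest events, a named endpoint component has neither a definition nor an output. The trial is open-label, so a term list written once the events are known could be selective, or could be taken to be.

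**Working it through.** No sample size, power or event figure is involved, so the check is a comparison of text.

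**Step 1. Are the two discontinuation outputs the same set?** Protocol section 10 deals with withdrawal of treatment and withdrawal from the study under separate headings, and says that a patient may stop treatment yet stay in follow-up. They are therefore different sets, and they can differ in both directions.

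**Step 2. Where would each kind of patient appear?** This assumes that the intolerance was recorded as an adverse event with onset after the first monotherapy dose.

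| Patient | SAP 18.1.2 table | Protocol 12.5.6 summary | General event tables (SAP 18.1.1) | Study withdrawals in disposition (SAP 9.1) |
|---|---|---|---|---|
| Stops monotherapy during run-in because of an event and leaves | Yes | Yes | Yes | Yes |
| Completes run-in, withdrawn at Visit 2 for intolerance, drug withdrawal recorded | Yes | Yes | Yes | Yes |
| Completes run-in, withdrawn at Visit 2 for intolerance, drug withdrawal **not** recorded | **No** | Yes | Yes | Yes |
| Stops drug because of an event but stays in the study | Yes | No | Yes | No |

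The third row is the gap. The other tables do not close it. Disposition carries no SOC or PT, and the general event tables do not show which events led to withdrawal.

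**Step 3. Is the third row possible under the protocol's own terms?** Protocol section 10 describes treatment withdrawal as not receiving the complete course, with no further planned dose. If the course is the 4-week run-in, the patient has completed it and no withdrawal need be recorded. If the course is the whole treatment plan, a planned dose was cancelled and withdrawal would be recorded. The documents do not settle which reading the eCRF follows.

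**Step 4. How many patients?** Protocol 12.2 plans 290 screened and 216 patients for the required sample, a planned loss of 290 − 216 = 74. That figure pools screen failures and all later drop-outs, and the documents do not split it. It gives no rate of intolerance at Visit 2 and no rate of miscoding, so no estimate follows. The lower bound is zero.

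**Step 5. Special-interest events.** They are named in the protocol synopsis and in sections 4, 8.2 and 12.4. They are absent from the summary list in protocol 12.5.6 and from SAP section 18. Neither document says which events qualify. SAP 18.1 ties its overall summary to the categories in its own subsections, so that summary does not supply the missing output. SAP 18.7 is weak evidence on its own, because special-interest events are a subset of adverse events and not a separate assessment. The absence rests on the list of subsections.

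**The case against.** A reader might infer that patients withdrawn for intolerance during run-in are not counted at all. The documents do not support that. The Safety population in SAP 5.3 takes in anyone with one dose of monotherapy. SAP 18.1.2 expressly covers monotherapy. SAP 18.1 gives run-in events a Monotherapy heading, under a rule that opens with "TEAEs that occurred or worsened on or after the date/time of the first administration of Monotherapy but before the date/time of the first administration of" and then names the combination as the cut-off. SAP 9.1 presents withdrawals for all patients. Nor has the discontinuation output been dropped: a closely related table by SOC and PT replaces it.

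It can also be argued that drug withdrawal is the natural entry at Visit 2, since the patient stops a drug that would otherwise have continued within the combination. That may be so, and the miss is possible rather than shown. But the table's completeness should not depend on a coding habit that neither document specifies.

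On special-interest events, the gap starts in the protocol, which never defines them and omits them from its own summary list. Any such event is still in the SOC and PT tables. Protocol 12.7 treats analyses not prespecified and run after lock as exploratory, which limits the harm of a late list. The SAP templates were not available, so a row there cannot be excluded. These points stand, and on its own this part would be little more than missing detail. It remains that protocol 12.7 assigns detailed description of endpoints and analyses to the SAP, and a named component has none.

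**Conclusion.** Both mismatches hold on the text and neither is declared. The consequence is limited: the discontinuation table can understate monotherapy intolerance among patients who complete run-in and are removed at Visit 2, and one component of the secondary safety endpoint has no definition or output. The number of patients affected cannot be estimated. The understatement rests on one assumption that the documents do not resolve, namely that some such events carry no drug-withdrawal action. Reporting of the safety objective is affected; the primary efficacy result is not. The change is worth making because the protocol already promises the output and the correction is cheap.

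**What to change.** 1. Add to SAP 18.1 a table of treatment-emergent events leading to discontinuation from the study, by SOC and PT and by Monotherapy and Combination Therapy. Identify the patients from the recorded study-withdrawal reason, including non-tolerance at Visit 2. Keep the 18.1.2 table alongside it. If a withdrawal for non-tolerance has no linked event, give the count in a footnote.
2. For special-interest events, either add an incidence table by phase or declare the removal of this component in SAP 3.3. If the table is added, draw the preferred-term list from the summaries of product characteristics, which protocol 9.6 makes the reference safety document, and fix it before database lock.
3. Record in SAP 3.3 any departure from protocol 12.5.6 that remains.

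The cost is SAP wording and at most two tables. Protocol section 10 already requires the date and specific reason for withdrawal in the eCRF. The documents do not show a link from that reason to a coded event, so the link may have to be made at data review. One limit remains: the SAP is dated 11 November 2022 and last patient out was planned for early December 2022, so a term list fixed now would be written with much open-label data already visible. Taking it from the reference safety documents reduces that discretion without removing it.
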